7.2. Definition of Adverse Events

AEs and grading criteria listed below are consistent in definitions in 21 CFR 312.32.

An AE is any noxious, unintended, or untoward medical occurrence that may appear or worsen in a participant during the study. It may be a new intercurrent illness, a worsening concomitant illness, an injury, or any concomitant impairment of the participant's health, including laboratory test values (as specified by the criteria below), regardless of etiology. A diagnosis or syndrome should be recorded on the AE page of the case report form (CRF) rather than the individual signs or symptoms of the diagnosis or syndrome.

An abnormal laboratory value is considered to be an AE if the abnormality:

- Results in discontinuation from the study;
- Requires treatment, modification/interruption of the study treatment dose, or any other therapeutic intervention; or
- Is judged to be of significant clinical importance.

Regardless of the severity grade, only laboratory abnormalities that fulfill a seriousness criterion need to be documented as an SAE.

If a laboratory abnormality is one component of a diagnosis or syndrome, then only the diagnosis or syndrome should be recorded as an AE. If the abnormality was not a part of a diagnosis or syndrome, then the laboratory abnormality should be recorded as an AE.

An AE with medically-attended visits (either in person or telemedicine visit) that are not routine visits for physical examination or vaccination, such as visits for hospitalization, an emergency room visit, or an otherwise unscheduled visit to or from medical personnel (medical doctor) for any reason, will be documented as a MAAE. MAAEs can also be SAEs and will follow the same serious adverse event criteria and collection guidelines noted in [Section 7.3](#).

Duration and Frequency for Collecting AE and SAE Information

In the phase 1 and phase 2 studies, solicited AEs will be recorded by the investigator for 7 days after each dose. In the phase 1 and phase 2 studies, unsolicited AEs will be recorded from the time of first dose of study treatment until 30 days after study intervention. All MAAEs and SAEs will be recorded by the investigator from the time of first dose of study treatment until 6 months after study intervention. For MAAEs/SAEs that are considered related to study treatment, those events should be reported at any time regardless of vaccine administration date or end of study visit date.

7.3. Definition of Serious Adverse Events

AEs and grading criteria listed below are consistent in definitions in 21 CFR 312.32. AEs can be further divided into solicited AEs and unsolicited AEs. Solicited AEs are those for which the study team will specifically query the participant whether they occurred. Unsolicited AEs are those events that the participant report occurring without being queried about the specific event.

An SAE is any AE that suggests a significant hazard or AE, whether or not considered to be related to study treatment. An SAE fulfills one or more of the following criteria:

- Results in death.
- Is life-threatening (ie, in the opinion of the Investigator, the participant is at immediate risk of death from the AE as it occurred).
- Requires in-subject hospitalization or prolongation of existing hospitalization (hospitalization is defined as an in-subject admission, regardless of length of stay).
- Results in persistent or significant disability or incapacity (a substantial disruption of the participant's ability to conduct normal life functions).
- Results in a congenital abnormality or birth defect.
- Is an important medical event that may jeopardize the participant or may require medical intervention to prevent one of the outcomes listed above. Important medical events are defined as those occurrences that may not be immediately life-threatening or result in death, hospitalization, or disability, but may jeopardize the participant or require medical or surgical intervention to prevent one of the other outcomes listed above. Medical and scientific judgment should be exercised in deciding whether such an AE should be considered serious.

7.4. Evaluation of Adverse Events

A qualified Investigator will evaluate all AEs and report their seriousness, severity/intensity, relationship to the study treatment, duration, action taken, and participant outcome.

7.4.1. Severity/Intensity

The severity/intensity of AEs and SAEs will be graded based upon the participant's symptoms in accordance with the Guidance for Industry: Toxicity Grading Scale for Healthy Adult and Adolescent Volunteers Enrolled in Preventive Vaccine Clinical Trials (2007).

AEs that are not defined in the Guidance for Industry: Toxicity Grading Scale for Healthy Adult and Adolescent Volunteers Enrolled in Preventive Vaccine Clinical Trials (2007) should be evaluated for severity/intensity according to the following scale:

- Grade 1 = Mild: transient or mild discomfort, no limitation in activity; no medical intervention/therapy required.
- Grade 2 = Moderate: mild to moderate limitation in activity, some assistance may be needed; no or minimal medical intervention/therapy required.
- Grade 3 = Severe: marked limitation in activity, some assistance usually required; medical intervention/therapy required, hospitalization possible.
- Grade 4 = Life threatening: extreme limitation in activity, significant assistance required; significant medical intervention/therapy required, hospitalization or hospice care probable.
- Grade 5 = Death: the event results in death.

It is important to distinguish between serious and severe AEs. Severity is a measure of intensity, whereas seriousness is defined by the criteria under [Section 7.3](#). An AE of severe intensity may not be considered serious. Seriousness, not severity, serves as a guide for defining regulatory obligations.

7.4.2. Relationship to the Investigational Product

The relationship between the administration of study treatment and the occurrence of an AE/SAE will be determined, as defined below:

- Not suspected/Not related: The temporal relationship of the AE or SAE to the study drug administration makes a causal relationship unlikely or remote, or other medications, therapeutic interventions, or underlying conditions provide a sufficient explanation for the observed event.
- Suspected/Related: The temporal relationship of the AE or SAE to the study drug administration makes a causal relationship possible, probable, or definite; and other medications, therapeutic interventions, or underlying conditions do not provide a sufficient explanation for the observed event.

7.4.3. Duration of Adverse Events

The Investigator will provide a record of the start date and stop dates for all AEs and SAEs.

An AE start date should be entered as the first date the participant experiences any signs or symptoms. If a later diagnosis is made, the date the symptom started is the start date rather than the date of the diagnosis.

For SAEs, the start date should be entered as the date the event first met serious criteria (see [Section 7.3](#) for definitions).

AEs and SAEs should have an end date that corresponds to the resolution of the event. SAEs will be followed until satisfactory resolution or until the site Investigator deems the event to be chronic or the adherence to be stable.

Please see the study-specific CRF data entry completion guidelines and SAE report completion guidelines for further instructions for capturing the start and stop dates of AEs and SAEs.

Changes in the severity of an AE will be documented to allow an assessment of the duration of the event at each level of severity. AEs characterized as intermittent require documentation of the onset and duration of each episode.

For 30 days after the last dose, at each study visit, the Investigator will inquire about the occurrence of AE/SAEs since the last visit or follow-up. From 30 days after the last dose to 6 months after the last dose, at each study visit, the Investigator will inquire about the occurrence of SAEs since the last visit or follow-up. Events will be followed for outcome information until resolution or stabilization.

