Solicited local and systemic reactogenicity AEs will be collected using diaries for 7 days following study intervention (ie, administration of vaccine). Unsolicited AEs will be recorded in a diary from time of vaccination until 30 days after study intervention. Medically attended adverse events (MAAEs) and SAEs will be recorded for 6 months after study intervention (related MAAEs and SAEs will be recorded at any time).

Immunogenicity analyses will be conducted by collecting serum and PBMC samples from individual participants before and after vaccinations to test for humoral- and cell-mediated immune responses. Neutralizing antibodies will be assessed.

Phase 2

In the phase 2 study, up to 120 previously vaccinated/infected additional participants will be enrolled. Participants in phase 2 will be randomized 1:1:1:1 to receive Janssen or Pfizer-BioNTech vaccine (control arm), the AAHI SC2 vaccine (experimental arm 1), or the AAHI-SC3 vaccine (experimental arms 2 and 3). Dose levels for the AAHI-SC2 and AAHI-SC3 vaccines will be as determined in the phase 1 study. Randomization will be stratified by age (18 to 55 years or > 55 years), by previous infection (previously infected or not), and by HIV status (positive or negative). Treatment arms are shown in Table 5.

Table 5: Phase 2 Previously Vaccinated/Infected Dosing Schedule

Treatment Arm	Participants	Vaccine	Dosing schedule	Dosage
Control arm	30	EUA or approved vaccine	Day 1	Per prescribing information
Experimental arm 1	30	AAHI-SC2	Day 1	TBD: As determined in phase 1 study
Experimental arm 2	30	AAHI-SC3	Day 1	TBD: As determined in phase 1 study
Experimental arm 3	30	AAHI-SC3	Day 1 and day 29	TBD: As determined in phase 1 study

In addition to dosing visits described above, all participants in all phases of the study will have follow up study visits for data collection.

The SRC will provide ongoing safety review in the phase 2 study. If a possible safety signal is detected, the SRC will determine if the event warrants stopping the trial, modifying the trial, or continuing without modification.

Solicited local and systemic reactogenicity AEs will be collected using diaries for 7 days following study intervention (ie, administration of vaccine). Unsolicited AEs will be recorded in

a diary from time of vaccination until 30 days after study intervention. MAAEs and SAEs will be recorded for 6 months after study intervention (related MAAEs and SAEs will be recorded at any time).

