3.3. Duration of Study

3.3.1. Duration of Treatment

For most participants, treatment will be confined to study day 1. For participants in experimental arm 3 of the phase 2 study, treatment will occur on day 1 and day 29.

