3.3.2. Duration of Follow-Up

Participants who receive study treatment will be followed by a health care professional until either death (by any cause) or for 1 year past first administration of vaccine.

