3.4.1.1. Primary Endpoints

- Incidence of MAAEs and SAEs through 1 week post final vaccine administration
- Incidence of MAAEs and SAEs through 30 days post final vaccine administration
- Incidence of MAAEs and SAEs through 6 months post final vaccine administration
- Incidence and severity of solicited local reactogenicity AEs through 1 week after each vaccine administration
- Incidence and severity of solicited systemic reactogenicity AEs through 1 week after each vaccine administration
- Incidence and severity of unsolicited AEs through 1 week post final vaccine administration

- Incidence and severity of unsolicited AEs through 30 days post final vaccine administration
- Incidence of abnormal changes of laboratory safety examinations
- Changes in vital signs

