6.3. Safety Assessments

All participants will be monitored for AEs during the study. Assessment of AEs will include the following parameters:

- All MAAEs and SAEs for 6 months after last vaccine administration (related MAAEs and SAEs at any time)
- Solicited local and systemic AEs via diary for 7 days after each vaccine administration (applicable to the phase 1 and phase 2 studies)
- Unsolicited AEs via diary from first dose of study treatment until 30 days after last vaccination (applicable to the phase 1 and phase 2 studies)
- Vital signs
- Body weight
- Physical examinations
- Hematology: CBC with differential
- Chemistry panel: Collection of whole blood for complete metabolic panel (CMP)
- Urinalysis: protein, glucose, and RBCs
- Pregnancy test.

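### Late safety questioning in Section 7.4.3 leaves out MAAEs, and in phase 2 arm 3 the day-180 contact comes 151 days after the last dose, short of the 6-month endpoint

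*Combined protocol and SAP*

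**What the plan says.** **Endpoints.** Section 3.4.1.1 lists as a phase 1 primary endpoint "Incidence of MAAEs and SAEs through 6 months post final vaccine administration". Section 3.4.2.2.1 lists the same item as a phase 2 secondary endpoint.

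**Recording rules.** Section 6.3 requires "All MAAEs and SAEs for 6 months after last vaccine administration (related MAAEs and SAEs at any time"). Section 7.2 has MAAEs and SAEs recorded "from the time of first dose of study treatment until 6 months after study intervention"; Section 3.1 uses the same end point. Neither of those two sections says which dose is meant.

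**Questioning rule.** Section 7.4.3 has two periods. In the first 30 days after the last dose the investigator asks about AEs and SAEs. From 30 days to "6 months after the last dose, at each study visit, the Investigator will inquire about the occurrence of SAEs since the last visit". MAAEs are not named in the second period.

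**Link between MAAEs and SAEs.** Section 7.2 says that MAAEs "will follow the same serious adverse event criteria and collection guidelines noted in" Section 7.3.

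**Schedule.** Section 3.3.1: "For participants in experimental arm 3 of the phase 2 study, treatment will occur on day 1 and day 29". Section 3.3.2 sets follow-up "for 1 year past first administration of vaccine", and Section 6.7.3 anchors end of study to the first injection too. After day 29, Table 10 has contacts at days 36 (a call for arm 3 only, footnote g), 60, 180 and 365. In-office AE collection is marked at days 1, 8, 22, 29 and 60. Days 180 and 365 are marked as telephone follow-up.

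**The concern.** An endpoint is only as complete as the questions put to participants. A non-serious clinic attendance four months after vaccination is an endpoint event in both phases. The unsolicited diary has ended by then (Section 6.3.2), and the one section that tells the investigator what to ask at later contacts mentions only SAEs. A site that follows that sentence literally need not ask about it.

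The second problem is one of anchoring. The endpoint runs from the final vaccine, but the visit calendar runs from the first. For single-dose participants the two nearly coincide. For arm 3 they differ by 28 days, and nothing in the schedule makes up the difference.

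The safety analysis is descriptive (Section 8.3.2), so the incidence counts are themselves the result. Events that nobody asks about cannot be recovered in the analysis.

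**Working it through.** The plan has no figure of its own to reproduce here. The check sets the rules side by side and then does date arithmetic on Table 10.

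**Part 1: which contacts lack a prompt for MAAEs (both phases)**

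- The SAE-only period starts at day 1 + 30 = 31 for single-dose participants and at day 29 + 30 = 59 for arm 3. Days 60 and 180 both fall inside it.
- Day 60: Table 10 schedules in-office AE collection. Section 7.2 defines a MAAE as an AE with a medically attended visit, so general AE collection there picks up MAAEs to that date.
- Day 180: telephone follow-up, with no AE collection marked. Only Section 7.4.3 governs the questions, and it names SAEs.
- Unprompted stretch: 180 − 60 = 120 days. As a share of a 6-month window assumed to be 180–183 days, 120/183 = 65.6% to 120/180 = 66.7%, about two-thirds.
- Section 7.3, the target of the cross-reference in Section 7.2, defines SAEs and lists seriousness criteria. It contains no inquiry schedule.
- Events left exposed: SAEs are asked about, and related MAAEs are recorded at any time (Section 6.3). What remains is non-serious MAAEs judged unrelated.

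**Part 2: reach of the day-180 contact (phase 2 arm 3 only)**

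Inputs: last dose on day 29 in arm 3 and day 1 elsewhere; contacts at days 180 and 365; 6 months assumed to be 180–183 days.

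| Quantity | Arm 3 | Single-dose arms |
|---|---|---|
| Days from last dose to the day-180 contact | 180 − 29 = 151 | 180 − 1 = 179 |
| End of 6-month window (study day) | 29 + 180 = 209 to 29 + 183 = 212 | 1 + 180 = 181 to 1 + 183 = 184 |
| Days of window after day 180 | 29 to 32 | 1 to 4 |

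- Difference between the columns: 179 − 151 = 28 days.
- Arm 3 share of the window not covered: 29/180 = 16.1% to 32/183 = 17.5%.
- Visit windows: the windows row of Table 10 is broken in the text available. If day 29 is ±3 and day 180 is ±7 (assumed), the arm 3 gap runs from 26 + 180 − 187 = 19 days to 32 + 183 − 173 = 42 days. It does not close.
- Next contact: day 365, which is 365 − 29 = 336 days after dose 2. The questioning period in Section 7.4.3 has ended by then, and no section tells the site to look back.
- Recall needed at day 365 for events on days 180–212: 365 − 212 = 153 to 365 − 180 = 185 days, about 5 to 6 months.

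All phase 1 cohorts receive a single dose, so Part 2 does not touch the phase 1 primary endpoint.

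**The case against.** The best defence is that the operative rule is in Sections 6.3 and 7.2, where all MAAEs and SAEs must be recorded to 6 months. An investigator under that duty has to ask, and the intent to treat MAAEs like SAEs is plain from Section 7.2. Section 7.4.3 mainly concerns dates and duration, and its omission may be editorial. Concomitant medications are reviewed at day 180, which gives an indirect prompt. CRF completion guidelines, which were not available, may add more. For arm 3, a day-365 call exists, related events are reportable at any time, and Section 7.5.2 requires SAEs to be reported within 24 hours of the investigator's knowledge.

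Most of that stands, and it limits the size of the problem. It does not remove it. The duty to record is intact, but the only explicit instruction on what to ask still omits MAAEs, and the cross-reference leads to a section with no procedure.

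A reader might infer more than the documents support:

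- *That MAAEs go unasked at day 60 as well as day 180.* Read alone, Section 7.4.3 covers both contacts, but Table 10 collects AEs at day 60.
- *That sites may stop arm 3 recording 28 days early, because Sections 3.1 and 7.2 name no dose.* Section 6.3 and both endpoint lists specify the last or final vaccine, which largely settles the anchor. This is an ambiguity to tidy.
- *That arm 3 events after day 180 are lost.* The recording duty and the day-365 call remain. What is missing is timely contact and a look-back instruction.
- *That arm 3 is biased against the other arms.* Section 8.3.1 plans no statistical comparison of the phase 2 arms, and no such bias is claimed here.

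**Conclusion.** The point holds in two limited parts.

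1. In both phases, Section 7.4.3 does not match the endpoints and recording rules it should serve. The practical gap is the day-180 contact, covering about days 60–180, and the events at risk are non-serious MAAEs judged unrelated.
2. In phase 2 arm 3 (30 participants), the schedule does not deliver the stated window. The day-180 contact is 151 days after dose 2, which leaves 29–32 days without a scheduled contact until day 365 (19–42 days under the assumed visit windows). The events at risk are unrelated MAAEs, and unrelated SAEs that the site has not otherwise learned of.

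Both are risks of under-ascertainment. Neither shows that data will be lost. The 151 and 179 days follow directly from the protocol. The length of the gap rests on taking 6 months as 180–183 days, and its range on visit windows of ±3 and ±7 days. CRF guidelines could reduce the risk in practice. A correction is worthwhile because the first part touches a phase 1 primary endpoint and the remedy is small.

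**What to change.** - **Section 7.4.3:** name MAAEs alongside SAEs in the sentence on the later questioning period.
- **Table 10:** state that the day-180 contact collects MAAEs and SAEs.
- **Sections 3.1 and 7.2:** say that the 6 months run from the last vaccine administration, to agree with Section 6.3 and the endpoints.
- **Arm 3:** have the existing day-365 contact ask about MAAEs and SAEs since day 180, and count those within 6 months of dose 2. The drawback is recall over about 5 to 6 months. Alternatively, add one arm-3-only call at 6 months after dose 2, as footnote g of Table 10 already does at day 36. The drawback is one more call for each of 30 participants.
- **Six months:** give it a day count, so that the window can be programmed.

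The cost is a few wording changes plus one added question or one added call. Sample size, dosing and laboratory work are unaffected.

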7.4.4. Outcome

The Investigator will report the outcome of the event for AEs and SAEs. AEs will be followed for 30 days after the participant's last dose of study treatment. Grade 3 or 4 AEs will be followed until resolution or stabilization. All SAEs that have not resolved upon discontinuation of the participant's participation in the study must be followed until recovered, recovered with sequelae, not recovered (death due to other cause), death (due to the SAE), lost to follow-up, or otherwise explained.

7.5. Reporting Procedures

The Investigator is required to ensure that the data on the AE and SAE report forms are accurate and consistent.

7.5.1. Reporting Procedures for Adverse Events

Any AE (as defined in [Section 7.2](#)) should be reported as an AE on the AE page of the CRF and in the participant's source documents.

Any medical condition that is present at the study participant's screening visit will be considered as baseline and not reported as an AE; however, if the study participant's condition deteriorates at any time during the study, it will be recorded as an AE.

7.5.2. Reporting Procedures for Serious Adverse Events

SAEs will be recorded on the study-specific SAE Report Form, the AE page of the CRF, and in the participant's source documents. All SAEs must be reported to Sponsor Drug Safety within 24 hours of the Investigator's knowledge of the event by email, fax, or other appropriate method using the SAE Report Form. This instruction pertains to initial SAE reports as well as any follow-up reports.

SAE Reporting Information:

Email: [contact]

[contact]

The Investigator will ensure that the data in the SAE report forms are accurate, and consistent with the evaluations described in [Section 7.4](#) above. The SAE report should provide a detailed description of the SAE and include summaries of hospital records and other relevant documents, which must be de-identified. The Investigator will report the action taken with study treatment as a result of any SAE and report if concomitant and/or additional treatments were given for the event. All SAEs that have not resolved upon discontinuation of the participant's participation in the study must be followed until recovered, recovered with sequelae, not recovered (death due to other cause), death (due to the SAE), lost to follow-up, or otherwise explained. Any follow-up data will be detailed in a subsequent SAE Report Form and sent to Sponsor Drug Safety. If a participant died and an autopsy has been performed, copies of the autopsy report and death certificate are to be sent to Sponsor Drug Safety as soon as these become available.

